9.7 Other analyses

Not applicable.

9.8 Interim analysis

One or more interim analyses may be conducted to support decision-making in relation to the current clinical study, the future of the sponsor's clinical development plan, or the long-term safety and efficacy of ligelizumab. Additional details will be provided in the SAP.

9.9 Sample size determination

9.9.1 Primary endpoint(s)

The expectation is that approximately 550 participants from the Study CQGE01G12301 and other QGE031 Phase III studies will enroll in this extension study, after accounting for an estimated drop-out rate of 15% during the core phase of the studies.

No hypothesis testing is planned in the extension study.

9.9.2 Secondary Endpoints

All participants will have the opportunity to receive ligelizumab during the study. This sample size is sufficient to yield adequate precision in estimating AE rates in this study. For example, if one percent of 200 participants has an AE, the exact 95% Clopper-Pearson confidence interval for the proportion of participants would be 0.12% to 3.6%. The table below gives the 95% confidence intervals for varying sample sizes and incidence rates, assuming approximately 200 or 300 subjects are in each treatment dose group.

Table 9-1 Precision Levels (95%) for sensitivity of safety incidence rate

Number of Participants	Event Rate (%)	95% Confidence Interval
200	1	(0.12%, 3.6%)
	2	(0.55%, 5%)
	3	(1.10%, 6.4%)
300	1	(0.21%, 2.9%)
	2	(0.74%, 4.3%)
	3	(1.40%, 5.6%)
550	1	(0.35%, 2.2%)
	2	(1.00%, 3.6%)
	3	(1.70%, 4.8%)

Confidence intervals generated using the exact Clopper-Pearson method.

Novartis

10 Supporting documentation and operational considerations

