2.1 Study rationale

This is a multi-center, double-blind, 3-year, extension study with a 16 week follow-up period which is designed to establish ligelizumab's long-term safety, and explore its long-term efficacy, in participants with food allergy who have completed the Phase III studies with ligelizumab in food allergy including (but not limited to) Study CQGE031G12301 (peanut allergy). This protocol is designed as a basket extension study, open to the participants from multiple planned Phase III "core" studies in addition to the Study CQGE031G12301. Of note, the present protocol is dedicated to include only peanut allergic patients from study CQGE031G12301. Future amendments will be submitted for approval to update study features, if needed, before the extension study CQGE031G12303B is opened to participants from future core studies other than study CQGE031G12301.

This study will generate data that should provide guidance relative to the long-term (chronic) use of ligelizumab in food allergic patients in terms of safety, efficacy, pharmacodynamics (PD), biomarkers, quality of life (QoL), and potential discontinuation from treatment. Indeed some of the important clinical points that this study will explore focus on:

- Longer-term (>1y) sustainability of ligelizumab efficacy
- CC
- Alignment with international guidelines (Muraro et al 2014) that recommend regular assessment of the underlying phenotype including the option to discontinue treatment (further supported by the analysis of the operating characteristics of several biomarkers that strengthen the decision making)
- A subset of participants will also be offered administration of study treatment at home either by the participant him/herself (self-administration) or by parent/caregiver following appropriate training at three visits in the clinic.

In addition, the 3-year treatment period of this study will also fulfill the Novartis commitment to provide post trial access (PTA) to the participants who have completed ligelizumab Phase III studies in food allergy. In case ligelizumab is not commercially available in some countries at completion of this study, every effort will be made to continue provision of ligelizumab for the participants in those countries that in the opinion of the investigator might still benefit from longer treatment with ligelizumab.

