6.1.3 Treatment arms/group

Participants will be assigned to one of the following two treatment arms depending on responder status in the previous study/ies) as per Section 4.1.1 and Section 4.1.2.

Each participant (except the MR participants undergoing conditional discontinuation) will receive two (2) SC injections every four weeks starting at Day 1.

- 1. ligelizumab 240 mg arm: 2 injections of 1.0 mL ligelizumab
- 2. ligelizumab 120 mg arm: 1 injection of 1.0 mL ligelizumab and 1 injection of 1.0 mL placebo

The assignment to receive 120 mg or 240 mg ligelizumab will be determined by treatment received during the previous study(ies). All participants (except the MR participants undergoing conditional discontinuation (Section 4.1.2)) will receive study drug (ligelizumab). There is no placebo arm.

Of note, based on CQGE031G12301 core study results, Novartis will assess the need to switch participants in CQGE031G12303B to a different dose than the one they were receiving in CQGE031G12301.

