9.3.2 Statistical model, hypothesis, and method of analysis

There is no pre-specified hypothesis for the primary endpoints, and no inferential analysis will be done for the primary endpoints.

Summary statistics will be provided.

Summaries will include: 1) the number and percentages of participants with at least one event (incidence rates); and 2) exposure-adjusted occurrence rates (the number of events per participant year of exposure). The following treatment-emergent AE summaries will be provided for the Safety Set 1 (SAF-1), presented by dose and cumulative duration of exposure:

- Overall, by primary system organ class and preferred term,
- Overall, by primary Standardized MedDRA Query (SMQ) and preferred term,
- Overall, by primary system organ class, preferred term and maximum severity,
- Suspected drug-related AEs by primary system organ class and preferred term,
- SAEs by primary system organ class and preferred term,
- AEs leading to permanent discontinuation of study-drug by primary system organ class and preferred term,
- Adverse events of special interest (AESI).

Other tables will be generated to summarize safety data for participants in SAF-1 who restarted study treatment after a protocol mandated interruption period (> 16weeks). Details will be provided in the SAP.

Summaries will be performed as well for non-TEAEs for participants who did not receive any study treatment doses during the extension study (SAF-2).

Separate summaries will be provided for study treatment-related adverse events, death, serious adverse events, and other significant adverse events leading to discontinuation. If a participant reported more than one AE with the same preferred term, the AE with the greatest severity will be presented. If a participant reported more than one AE within the same primary system organ class, the participant will be counted only once with the greatest severity at the system organ class level, where applicable.

Other safety analyses (laboratory data, vital signs, ECG) are described in Section 9.4.2.

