CRF Case Report/Record Form (paper or electronic)

CRO Contract research organization

CSR Clinical study report
CV Coefficient of variation

DBL Database Lock

DBPCFC Double Blind Placebo Controlled Food Challenge

DLS Dose limiting symptom
EAIR Exposure adjusted
ECG Electrocardiogram

eCRF Electronic case report form
eCRS Electronic case retrieval strategy

EOS End of study

FAIM Food Allergy Independent Measure
FAQLQ Food Allergy Quality of Life Questionnaire

FAS Full Analysis Set

FcεRI IgE (high affinity) receptor

h Hour HR Heart rate

HRQoL Health-Related Quality of Life

IgE Immunoglobulin E (specific and un-specific for the study allergen)

IgG Immunoglobulin G
IS Independent Statistician

L Liter

CCI

MedDRA Medical dictionary for regulatory activities

mg Milligram(s)
mL Milliliter(s)
mm Millimeter

mmHg Blood pressure unit millimeters of mercury

MR Maximum responder

ms Millisecond

OFC Oral Food Challenge PD Pharmacodynamic(s)

CC

PRO	Patient Reported Outcomes
PT	Preferred term
q4W	Every 4 weeks
RR	Responder rate
SAE	Serious Adverse Event
SAF	Safety analysis set
SAP	Statistical analysis plan
SC	Subcutaneous
SCq4W	Subcutaneous injection every 4 weeks
SD	Standard deviation
CCI	
SMQ	Standardized MedDRA Query
SOC	System organ class
SPT	Skin Prick Test
TEAE	Treatment-emergent adverse events
TESAE	Treatment-emergent serious adverse events
Total IgE	Drug-bound and free IgE
μL	Microliter

1 Introduction

The purpose of this Statistical Analysis Plan (SAP) is to describe the statistical analyses mentioned in version of the Phase 3 study CQGE031G12303B protocol. This document covers the statistical and analytical plans for the Clinical Study Report (CSR).

After thorough consideration, Novartis decided to terminate the study early. This was a consequence of a broader Novartis company strategic decision and was by no means due to the detection of any potential safety signal. Due to the early termination, the scope of analysis will be limited.

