2.5.2.2 Adverse Events (AEs)

The following treatment-emergent AE summaries will be provided by overall and by treatment group for the Safety Set 1 (SAF-1), presented by dose and cumulative duration of exposure:

- Overview of all TEAEs: Number of participants with at least one (Any AE, Any SAE, Any AE related to study drug, Any AE leading to discontinuation of study treatment, Deaths etc.)
- TEAEs by primary system organ class and preferred term,
- TEAEs by primary Standardized MedDRA Query (SMQ) and preferred term,
- TEAEs by primary system organ class, preferred term and maximum severity,
- TESAEs by primary system organ class and preferred term,
- TEAEs leading to permanent discontinuation of study-drug by primary system organ class and preferred term,
- Treatment Emergent Adverse events of special interest (AESI),
- Study treatment-related adverse events by primary system organ class and preferred term,
- Deaths by primary system organ class and preferred term including listing of deaths,

If a participant reported more than one AE with the same preferred term, the AE with the greatest severity will be presented. If a participant reported more than one AE within the same primary system organ class, the participant will be counted only once with the greatest severity at the system organ class level, where applicable.

Separate summaries will be provided for study treatment-related adverse events, death, serious adverse events, and other significant adverse events leading to discontinuation.

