2.14 Interim analysis

Not applicable.

3 Sample size calculation

The expectation is that approximately 200 participants from the study CQGE01G12301 will enroll in this extension study.

4 Change to protocol specified analyses

5 Appendix

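### Protocol 9.9.2 bases adverse-event precision on 200 or 300 per dose, but SAP Section 3 expects about 200 in total and does not restate it

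*Protocol*

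**What the plan says.** Protocol 9.9.1 expects "approximately 550 participants from the Study CQGE01G12301 and other QGE031 Phase III studies will enroll in this extension study" and plans no hypothesis test. Protocol 9.9.2 calls that size sufficient for estimating adverse-event rates. It supports this with Table 9-1, which gives exact intervals at event rates of 1%, 2% and 3% for 200, 300 and 550 participants, "assuming approximately 200 or 300 subjects are in each treatment dose group". The total of 550 also stands in the protocol summary and in Section 5.

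Protocol 2.1 narrows entry: "the present protocol is dedicated to include only peanut allergic patients from study CQGE031G12301". Participants from other core studies are left to future amendments. Protocol 6.1.3 sets out two dose groups, 120 mg and 240 mg, carried over from the core study.

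The whole visible content of SAP Section 3 is that "approximately 200 participants from the study CQGE01G12301 will enroll in this extension study". It gives no number per dose, no interval and no statement on precision. SAP 2.5.2.2 nevertheless plans the adverse-event summaries to be "provided by overall and by treatment group for the Safety Set 1 (SAF-1), presented by dose", and SAP 2.5.1 puts all safety listings and tables by dose.

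**The concern.** Safety is the primary objective and nothing is tested, so the precision statement in protocol 9.9 is the only visible justification for the study's size. Its per-dose premise needs at least 2 × 200 = 400 participants. The SAP expects about half of that.

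A reader of 9.9 would take each dose column of the safety tables to support the intervals in Table 9-1. With about 200 participants over two doses, the intervals per dose are clearly wider, and an absence of events in one dose group rules out much less. That matters most for uncommon events such as anaphylaxis, where the main question is what rate zero events can exclude.

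**Working it through.** **Inputs.** Exact two-sided 95% Clopper-Pearson limits (protocol Table 9-1); group sizes 200, 300 and 550 (same table); total of about 200 (SAP Section 3); two doses (protocol 6.1.3). The split between doses is not given. An equal split is assumed, with 80/120 and 67/133 as a range.

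**Formulas.** For x events in n participants, the lower limit is the 0.025 quantile of Beta(x, n − x + 1) and the upper limit is the 0.975 quantile of Beta(x + 1, n − x). For x = 0 the upper limit is 1 − 0.025^(1/n). The chance of seeing at least one event at a true rate p is 1 − (1 − p)^n.

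**Step 1: the plan's own table.** All nine rows reproduce at two significant figures.

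| n | 1% | 2% | 3% |
|---|---|---|---|
| 200 | 0.121 to 3.565 | 0.548 to 5.041 | 1.109 to 6.415 |
| 300 | 0.207 to 2.894 | 0.737 to 4.302 | 1.381 to 5.618 |
| 550 | 0.348 to 2.235 | 1.003 to 3.550 | 1.741 to 4.792 |

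(Limits in %. The 550 row at 1% and 3% uses fractional counts, 5.5 and 16.5.)

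**Step 2: can either dose reach 200?** If n₁ + n₂ = 200 and both groups contain participants, each is below 200. This needs no assumption about the split.

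**Step 3: per-dose limits at an equal split, n = 100.**

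| Events | Rate | n = 100 | Table 9-1, n = 200 |
|---|---|---|---|
| 1 | 1% | 0.025% to 5.446% | 0.12% to 3.6% |
| 2 | 2% | 0.243% to 7.038% | 0.55% to 5% |
| 3 | 3% | 0.623% to 8.518% | 1.10% to 6.4% |

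At 1% the width is 5.446 − 0.025 = 5.421 points. For n = 200 it is 3.565 − 0.121 = 3.444 (ratio 1.6), and for n = 300 it is 2.894 − 0.207 = 2.687 (ratio 2.0).

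**Step 4: zero events.** The upper limit at n = 100 is 1 − 0.025^(1/100) = 3.62%, against 1.83% at 200 and 1.22% at 300. For unequal splits it is 4.51% and 3.03% (80/120), or 5.36% and 2.74% (67/133).

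**Step 5: chance of at least one event at a true 1% rate.** 1 − 0.99^100 = 63%, against 87% at 200 and 95% at 300.

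**Step 6: both doses pooled.** With 200 treated, the 200 row stands and zero events exclude rates above 1.83%. This is a best case: under protocol 9.3.2, participants who never receive an extension dose belong to SAF-2, while the treatment-emergent summaries use SAF-1. If SAF-1 were 180 or 160 (illustrative assumptions), the zero-event limit would be 2.03% or 2.28%.

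**The case against.** The strongest reply is that the two totals describe different things. The 550 is for the whole basket of core studies, and the 200 is for one of them. The basket remains the stated design, and inclusion criterion 2 still refers to any Phase III food allergy study of the drug. The SAP was also written after the decision to stop: "Due to the early termination, the scope of analysis will be limited". On this view the 550 is a planning figure overtaken by events, and Table 9-1 contains no calculation error.

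Most of this is fair. The table is right, and the 550 was coherent for a basket. But Section 9.9 was left unchanged in the same protocol version that restricts entry to one study. SAP Section 3 does not say whether its 200 results from the termination. Whatever the cause, the per-dose precision is not delivered.

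Three other points limit the weight. The analysis is descriptive, and SAP 2.5.2.1 plans exact Poisson intervals for the exposure-adjusted rates, so achieved precision will be visible for those rates. The per-dose sizes used here are assumed. And the available copy of the SAP shows no text under Section 4 and lacks much of Sections 2.1 to 2.3, so an explanation there cannot be excluded. The statement about what is missing applies to SAP Section 3 only.

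**Conclusion.** The concern holds. With about 200 participants over two doses, the group sizes assumed in protocol 9.9.2 cannot be met for either dose, and the 300 and 550 rows of Table 9-1 no longer describe this study. The 200 row and its worked example remain valid for the pooled summary only, provided all 200 are treated.

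At an equal split, the per-dose interval at a 1% rate is about 1.6 times as wide as the plan states for 200, and the rate that zero events can exclude roughly doubles, from 1.8% to 3.6%. These magnitudes depend on the assumed split; the conclusion that each dose falls below 200 does not. The consequence is limited, because no hypothesis, decision rule or planned analysis changes. It should be corrected as a matter of accurate reporting.

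**What to change.** Reconcile protocol 9.9 with SAP Section 3. As the study has been terminated early, this can be done in SAP Section 3 and the study report without a protocol amendment:

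- State the expected or actual SAF-1 count for each dose and overall.
- Add exact 95% intervals for those counts at 1%, 2% and 3%, together with the upper limit for zero events.
- Say that the 200 row of protocol Table 9-1 applies to the doses pooled, and that its 300 and 550 rows no longer apply.
- Limit the claim of adequate precision to what those counts support.
- Say whether the 200 reflects the single-study entry limit, the early termination or both, and note that it replaces the 550 given in the protocol summary and Sections 5 and 9.9.1.

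The cost is a few sentences and one small table, with no extra participants and no change to any analysis. The only downside is that the stated precision becomes less favourable.

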10.1 Appendix 1: Regulatory, ethical, and study oversight considerations

10.1.1 Regulatory and ethical considerations

This study will be conducted in accordance with the protocol and with the following:

- Consensus ethical principles derived from international guidelines including the Declaration of Helsinki and Council for International Organizations of Medical Sciences (CIOMS) international ethical guidelines
- Applicable ICH Good Clinical Practice (GCP) guidelines
- Applicable laws and regulations

The protocol, protocol amendments, ICF, Investigator's Brochure, and other relevant documents (e.g., advertisements) must be submitted to an Institutional Review Board/Independent Ethics Committee (IRB/IEC) by the Investigator and reviewed and approved by the IRB/IEC before the study is initiated.

Any amendments to the protocol will require IRB/IEC approval before implementation of changes made to the study design, except for changes necessary to eliminate an immediate hazard to study participants.

Protocols and any substantial amendments/modifications to the protocol will require health authority approval prior to initiation except for changes necessary to eliminate an immediate hazard to study participants.

The Investigator will be responsible for the following:

Signing a protocol signature page confirming his/her agreement to conduct the study in accordance with these documents and all of the instructions and procedures found in this protocol and to give access to all relevant data and records to Novartis monitors, auditors, Novartis Quality Assurance representatives, designated agents of Novartis, IRBs/IECs, and regulatory authorities as required

Providing written summaries of the status of the study to the IRB/IEC annually or more frequently in accordance with the requirements, policies, and procedures established by the IRB/IEC

Notifying the IRB/IEC of SAEs or other significant safety findings as required by IRB/IEC procedures

Providing oversight of the conduct of the study at the site and adherence to requirements of 21 CFR, ICH guidelines, the IRB/IEC, European regulation 536/2014 for clinical studies (if applicable), European Medical Device Regulation 2017/745 for clinical device research (if applicable), and all other applicable local regulations

Inform Novartis immediately if an inspection of the clinical site is requested by a regulatory authority

This clinical study was designed and shall be implemented, executed and reported in accordance with the ICH Harmonized Tripartite Guidelines for Good Clinical Practice, with applicable local regulations (including European Clinical Trial Regulation 536/2014, US CFR 21), and with the ethical principles laid down in the Declaration of Helsinki.

10.1.2 Informed consent process

The Investigator or his/her representative will explain the nature of the study, including the risks and benefits, to the participant or their legally authorized representative (defined as parent/caregiver) and answer all questions regarding the study.

Participants must be informed that their participation is voluntary. Participants or their legally authorized representatives will be required to sign a statement of informed consent that meets the requirements of 21 CFR 50, local regulations, ICH guidelines, privacy and data protection requirements, where applicable, and the IRB/IEC or study center.

Informed consent must be obtained before conducting any study-specific procedures (e.g., all of the procedures described in the protocol). The process of obtaining informed consent must be documented in the participant source documents.

The medical record must include a statement that written informed consent was obtained before the participant was enrolled in the study and the date the written consent was obtained. The authorized person obtaining the informed consent must also sign the ICF.

A copy of the ICF(s) must be provided to the participant or their legally authorized representative.

The ICF will contain a separate section that addresses the use of remaining mandatory samples for optional additional research. The Investigator or authorized designee will explain to each participant the objectives of the additional research. Participants will be told that they are free to refuse to participate and may withdraw their consent at any time and for any reason during the storage period. A separate signature will be required to document a participant's agreement to allow any remaining specimens to be used for additional research. Participants who decline to participate in this optional additional research will document this.

Eligible participants may only be included in the study after providing (witnessed, where required by law or regulation), IRB/IEC-approved informed consent.

If applicable, in cases where the participant's representative(s) gives consent (if allowed according to local requirements), the participant must be informed about the study to the extent possible given his/her level of understanding. If the participant is capable of doing so, he/she must indicate agreement by personally signing and dating the written informed consent document.

Information about common side effects already known about the investigational treatment can be found in the Investigator's Brochure (IB). This information will be included in the participant informed consent and should be discussed with the participant upon obtaining consent and also during the study as needed. Any new information regarding the safety profile of the investigational drug that is identified between IB updates will be communicated as appropriate, for example, via an Investigator notification or an aggregate safety finding. New information might require an update to the informed consent and then must be discussed with the participant.

The following informed consents are included in this study:

- Main study consent, which also includes:
 - A subsection that requires a separate signature for the 'Optional Consent for Additional Research' to allow future research on data/samples collected during this study
- Parent/Guardian study consent
- Child Assent for ages 6-11 years
- Adolescent Assent for ages 12-17 years
- As applicable, Pregnancy Outcomes Reporting Consent for female participants

If a minor participant reaches the age of legal majority in the course of the study, he/she/they must be re-consented as an adult.

A copy of the approved version of all consent/assent forms must be provided to Novartis after IRB/IEC approval.

As per Section 4.5, during a public health emergency as declared by local or regional authorities i.e., pandemic, epidemic or natural disaster, that may challenge the ability to obtain a standard written informed consent due to limits that prevent an on-site visit, Investigator may conduct the informed consent discussion remotely (e.g., telephone, videoconference) if allowable by a local health authority.

Guidance issued by local regulatory bodies on this aspect prevail and must be implemented and appropriately documented (e.g., the presence of an impartial witness, sign/dating separate ICFs by trial participant and person obtaining informed consent, etc.).

